### 6.2 Handling of Missing Data

No imputation of missing data will be performed. Reasonable efforts will be made to obtain complete data for all patients. Missing observations, however, will occur due to patients lost to follow-up or noncompliance with required assessments. The reasons for missing data will be evaluated (e.g. patient is deceased, lost to follow up, missed visit, etc.). In addition, the distribution of prognostic factors between patients with data and those without data will be evaluate any potential sources of bias. Any missing observations will be described in detail and evaluated for assessment of possible bias.

### 7. SUMMARY OF BASELINE INFORMATION

### 7.1 Patient Enrollment and Accountability

The patient enrollment table will include both ITT and mITT populations. Patients from each site will be summarized separately. The patient disposition table will include total number of patients divided into the following categories: visit not yet due, death, explant, withdrew from study, lost to FU, visit completed, and visit not performed. Patients are considered eligible for follow-up if their visit window is open and prior to FU visit window, they are alive, not explanted, did not withdraw from study, and are not lost to FU. Each follow-up visit will have its own disposition section.

### 7.2 Demographics and Baseline Characteristics

The demographics and baseline characteristics table will contain descriptive summaries of age, sex, race, height, weight, resting blood pressure, STS mortality score, NYHA class, and KCCQ.

THIS DOCUMENT CONTAINS CONFIDENTIAL AND PROPRIETARY INFORMATION OF EDWARDS LIFESCIENCES, LLC. IT MUST NOT BE REPRODUCED OR DISCLOSED TO THIRD PARTIES WITHOUT PRIOR WRITTEN PERMISSION OF EDWARDS LIFESCIENCES, LLC. (This template is required by )

Revision Date: February 28, 2019		Rev		For Use Only by Affiliates of Edwards Lifesciences	Page 11 of 18	
Edwards	Title	Statistical Analysis Plan	for	ACTIVE	2017-05	

### 7.3 Medical History and Prior Intervention

The medical history table will include patient counts of various conditions and interventions available from the CRF.

#### 7.4 Baseline Risk Assessments

The baseline risk assessment table will include patient counts of various risk factors available from the CRF.

#### 7.5 **Procedural Information**

The procedure information table will contain descriptive summaries of procedure time, device disposition, number of patients permanently implanted, Cardioband implant size, and number of anchors.

### 8. STATISTICAL ANALYSIS OF STUDY ENDPOINTS

### 8.1 Co-Primary Hypothesis 1

H0:  $P_{Device}(T=1) - P_{Control}(T=1) = 0$ H1:  $P_{Device}(T=1) - P_{Control}(T=1) \neq 0$ 

where

H₀	= Null hypothesis
H1	= Alternative hypothesis
P Device	= Proportion of patients in the Device group with $MR \le 2+$ at 1 year
P Control	= Proportion of patients in the Control group with MR $\leq$ 2+ at 1 year
Т	= Time (years)

The co-primary hypothesis 1 tests the superiority in reducing MR of the Device group relative to the Control group via Chi-Square test for two independent proportions with two-sided alpha = .05. Co-primary efficacy endpoint 1 must meet statistical significance in order to proceed to co-primary efficacy endpoints 2. This approach does not require any adjustment for multiplicity.

### 8.2 Co-Primary Hypothesis 2

 $H_0$ : None of the four co-primary endpoints 2 are improved by treatment  $H_1$ : At least one of the four co-primary endpoints 2 is improved by treatment

- i. Time to all-cause death within the first year
- ii. Number of heart failure hospitalizations within the first year
- iii. Improvement in Six Minute Walk Test (6MWT) at 1 year relative to baseline (≥ 40 meters improvement)
- iv. Improvement in Kansas City Cardiomyopathy Questionnaire (KCCQ) at 1 year relative to baseline (≥ 10 points improvement)

The co-primary hypothesis 2 tests the superiority of the Device group relative to the Control group for the hierarchical sequence of the four co-primary endpoints 2 via the Finkelstein-Schoenfeld test (Finkelstein and Schoenfeld, 1999). The Finkelstein-Schoenfeld test is a generalization of the Gehan Wilcoxon test. Each patient pair is compared in descending order of the endpoints until one member of the pair shows superiority. While the example comparison given in the table below shows a Device patient being compared to a Control patient it should be noted that a pairwise comparison is made for every patient in Device group versus every patient in Control group.

THIS DOCUMENT CONTAINS CONFIDENTIAL AND PROPRIETARY INFORMATION OF EDWARDS LIFESCIENCES, LLC. IT MUST NOT BE REPRODUCED OR DISCLOSED TO THIRD PARTIES WITHOUT PRIOR WRITTEN PERMISSION OF EDWARDS LIFESCIENCES, LLC. (This template is required by DOC.))

### 2017-05 Statistical Analysis Plan |

| 1.0 | 7/16/2019

Edwards	Revision Date: February 28, 2019		Rev		For Use Only by Affiliates of Edwards Lifesciences	Page 12 of 18
	Title	Statistical Analysis Plan for ACTIVE 2017-05				

#### Table 1. Hierarchy of co-primary endpoints 2

Comparison of each potential patient pair	How Event is
(e.g. 1 from Device group and 1 from Control group)	Assessed
Step 1	
If 1 or both patients die due to cardiovascular (CV) cause	
Patient in Device group dies first due to CV cause	Favors Control
Patient in Control group dies first due to CV cause	Favors Device
Both patients die on the same day due to CV cause	Go to Step 2
If neither of the patients die due to CV cause	Go to Step 2
Step 2	
If no ranking yet available	
Patient in Device group had more heart failure hospitalizations	Favors Control
Patient in Control group had more heart failure hospitalizations	Favors Device
Both patients had equal number heart failure hospitalizations	Go to Step 3
Step 3	
If no ranking yet available	
Patient in Device group but not patient in Control group improved 6 minutes walking	Favors Davisa
distance ≥ 40 meters compared to baseline	Favois Device
Patient in Control group but not patient in Device group improved 6 minutes walking	Favors Control
distance ≥ 40 meters compared to baseline	
Both patients improved 6 minutes walking distance ≥ 40 meters compared to baseline	Go to step 4
Neither of the patients improved 6 minutes walking distance ≥ 40 meters compared to	Go to step 4
baseline	
Step 4	
If no ranking yet available	
Patient in Device group (but not Control) improved KCCQ score ≥10 points compared to	Eavors Device
baseline	Favois Device
Patient in Control group (but not Device)improved KCCQ score ≥10 points compared to	Favors Control
baseline	
Both patients improved KCCQ score ≥10 points compared to baseline	Tie
None of the patients improved KCCQ score $\geq 10$ points compared to baseline	Tie

The following rules are applied with the pairwise comparative outcome assessment:

- If any one of the patients in a patient pair is missing data for a variable included in the hierarchy then the pair will be considered a tie in regards to that variable/level and will proceed to the next level in the hierarchy.
- The time dependent events are censored at exactly 1 year after randomization.
- Patients who are censored during the first year (includes patients who are lost to follow-up as well as patients who die due to non-cardiovascular causes) will be compared to other patients using available data up until the time at which the patient was censored. In other words, the number of heart failure hospitalizations up until the censoring time will be compared between the patient pair.
- Inclusion of hospitalizations is based on adjudication by the Clinical Events Committee (CEC).
- The index hospitalization for Edwards Cardioband System implant in patients randomized to Device group is not counted as heart failure related hospitalization. However, if the hospital stay is prolonged beyond 5 days because of a heart failure (HF) complication, it is counted as a HF-related hospitalization. This rule is also applies to surgical mitral annuloplasty or replacement that is performed during follow-up in patients randomized to Control.
- Hospitalizations beginning prior to the exact 1 year time point are counted for analysis of frequency of hospitalization.

THIS DOCUMENT CONTAINS CONFIDENTIAL AND PROPRIETARY INFORMATION OF EDWARDS LIFESCIENCES, LLC. IT MUST NOT BE REPRODUCED OR DISCLOSED TO THIRD PARTIES WITHOUT PRIOR WRITTEN PERMISSION OF EDWARDS LIFESCIENCES, LLC. (This template is required by DOC))

	2017-05 Sta	tistical Analysis Plan			1.0   7/16/20	19
$\mathbb{P}$	Revision Date: Febr	uary 28, 2019	Rev		For Use Only by Affiliates of Edwards Lifesciences	Page 13 of 18
Edwards	Title	Statistical Analysis Plan for ACTIVE 2017-05				

- The 6MWT and KCCQ data from the 1-year visit are used regardless of whether the visit is before or after the exact 1 year time point.
- If clinical follow-up of one or both patients is censored, the pairwise outcome assessment is performed on the basis of those events that occurred during the smaller of the two follow-up times. For example, if a Control patient experiences an event on a particular day, and the Device patient is censored on that day or a later day, then the pair favors Device.

The Finkelstein-Schoenfeld method is a simple non-parametric statistical test for analyzing the impact of treatment which combines multiple events (e.g., death and hospitalizations) with longitudinal measures of clinical effect (e.g., 6MWT and KCCQ). The test is based on a Wilcoxon rank sum test. We define a score,  $\mu_{ij}$ , which is chosen to reflect whether patient i has had the more favorable outcome than patient j by following the hierarchy of scoring provided in table 1. If one of the patients has the more favorable outcome, his score is +1 and the other patient has a score of -1. If it is not possible to assign either patient as having the better outcome, then both patients get a score of 0.

This is a score test based on the sum of scores for the Device group. Suppose there are N total patients in the trial, let  $D_i = 1$  for patients in Device group and  $D_i = 0$  for patients in the Control group. Using the  $\mu_{ij}$  for every pair of patients defined above, we assign a score to each patient,  $U_i = \sum_{i \neq j} \mu_{ij}$ . The test is now based on

$$T = \sum_{i=1}^{N} U_i D_i.$$

Finkestein and Schoenfeld refers to this test as the generalization of the Gehan Wilcoxon (GGW) test. The null hypothesis is that none of the endpoints in table 1 are different between Device and Control group. The alternative hypothesis is that at least one endpoint in table 1 is different between Device and group.

Let m be the number of patients in the Device group. The mean of T is zero and its variance is

$$V = \frac{m(N-m)}{N(N-1)} (\sum U_i^2).$$

The hypothesis of interest is tested by comparing  $L = \frac{T}{\sqrt{V}}$  to the normal distribution. Hence, we are looking for a z-score that is indicative of a significant difference (p < .05) between the Device and Control groups.

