5 STUDY ENDPOINTS

5.1 Co-Primary Efficacy Endpoints (evaluated at 1 year)

- Co-primary endpoint I:
 - 1. Prevalence of MR \leq 2+ at one year.
- Co-primary endpoint II:

Hierarchical comparison between the Device and Control groups using Finkelstein-Schoenfeld methodology:

- 1. Time to all cause death
- 2. Number of heart failure hospitalizations
- 3. Improvement in 6 Minute Walk Test (6MWT) vs. baseline (≥ 40 meters improvement)
- Improvement in Kansas City Cardiomyopathy Questionnaire (KCCQ) at one year vs. baseline (≥ 10 points improvement)

The co-primary endpoints will be analyzed in a hierarchical order where the co-primary endpoint I must meet statistical significance in order to proceed to co-primary endpoint II. This approach does not require any adjustment for multiplicity. The co-primary efficacy endpoints were chosen in order to capture the ability of the Edwards Cardioband System to effectively reduce MR (co-primary endpoint I) as well as its ability to improve clinical outcomes through reducing MR (co-primary endpoint II).

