13.4.2 Analysis of the Primary Endpoints (Efficacy)

The co-primary endpoints will be analyzed in a hierarchical order where endpoint I must meet statistical significance in order to proceed to endpoint II. This approach does not require any adjustment for multiplicity.

Co-primary endpoint I

The proportion of patients who meet the criteria for reduction of mitral regurgitation $(MR \le 2+)$ at one year follow-up.

The comparison of co-primary endpoint I between Device and Control groups will be performed using a Chi-Square-test for two independent proportions.

Co-primary endpoint II

Conditional on the first co-primary endpoint meeting statistical significance, co-primary endpoint II will be analyzed using the non-parametric method described by Finkelstein and Schoenfeld. Briefly, each patient pair is compared in descending order of the endpoints until one member of the pair shows superiority. As specified above, these endpoints are:

- 1. Time to all-cause death within the first year
- 2. Number of heart failure hospitalizations within the first year
- 3. Improvement of 6-Minute Walk Test at one year vs. baseline (≥ 40 meters improvement)
- 4. Improvement in Kansas City Cardiomyopathy Questionnaire (KCCQ) score at one year vs. baseline (≥10 point improvement).

The specifics of the procedure will be provided in greater detail within the statistical analysis plan (SAP).

The Finkelstein-Schoenfeld method starts by a comparative outcome assessment for all patient pairs. While the example comparison given in the table below shows a Device patient being compared to a Control patient it should be noted that a pairwise comparison is made for every patient versus every other patient.

Comparison of each potential patient pair	How Event is
(e.g. 1 from Device group and 1 from Control group)	Assessed
Step 1	
If 1 or both patients die due to all-cause	
Patient in Device group dies first due to all-cause	Favors Control
Patient in Control group dies first due to all-cause	Favors Device
Both patients die on the same day due to all-cause	Go to Step 2
If neither of the patients die due to all-cause	Go to Step 2

Comparison of each potential patient pair	How Event is
(e.g. 1 from Device group and 1 from Control group)	Assessed
Step 2	
If no ranking yet available	
Patient in Device group had more hospitalizations** for HF	Favors Control
Patient in Control group had more hospitalizations** for HF	Favors Device

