### 3.3 **Primary Efficacy Endpoints (1 Year)**

- a. Co-primary efficacy endpoint 1: Prevalence of MR  $\leq$  2+ at 1 year
- b. Co-primary efficacy endpoint 2:
  - i. Time to all-cause death
  - ii. Number of heart failure hospitalizations
  - iii. Improvement in Six Minute Walk Test (6MWT) relative to baseline (≥ 40 meters improvement)
  - iv. Improvement in Kansas City Cardiomyopathy Questionnaire (KCCQ) relative to baseline (≥ 10 points improvement)

Co-primary efficacy endpoint 1 must meet statistical significance in order to proceed to co-primary efficacy endpoints 2. This approach does not require any adjustment for multiplicity. The co-primary efficacy endpoints were chosen in order to capture the ability of the Edwards Cardioband System to effectively reduce MR (co-primary endpoint 1) and improve clinical outcomes (co-primary endpoints 2).

THIS DOCUMENT CONTAINS CONFIDENTIAL AND PROPRIETARY INFORMATION OF EDWARDS LIFESCIENCES, LLC. IT MUST NOT BE REPRODUCED OR DISCLOSED TO THIRD PARTIES WITHOUT PRIOR WRITTEN PERMISSION OF EDWARDS LIFESCIENCES, LLC. (This template is required by DOC

	2017-05 Sta	tistical Analysis Plan I			1.0   7/16/20	19
E	Revision Date: Febr	uary 28, 2019	Rev		For Use Only by Affiliates of Edwards Lifesciences	Page 6 of 18
Edwards	Title	Statistical Analysis Plan	for	ACTIVE	2017-05	

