### 10. CHANGES FROM PROTOCOL SPECIFIED ANALYSES

The only difference between this SAP 3.0 and protocol rev E is that updated definition of enrolled population for roll-in patients is more meaningful from a device/procedure evaluation perspective. It will be included in future protocol updates.

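### SAP Table 1 scores only cardiovascular death at the top level of co-primary endpoint II, which both documents define as all-cause death, and SAP 10 lists no such change

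*SAP*

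**What the plan says.** The endpoint definitions agree. Protocol 5.1 lists "Time to all cause death" as level 1 of co-primary II, SAP 3.3 lists "Time to all-cause death", and the list in SAP 8.2 gives "Time to all-cause death within the first year". Step 1 of the pairwise table in Protocol 13.4.2 matches: "If 1 or both patients die due to all-cause".

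SAP 8.2, Table 1 does not match. Its Step 1 opens "If 1 or both patients die due to cardiovascular (CV) cause", and all five lines of the step are restricted to cardiovascular death. A pair with no cardiovascular death goes on to heart failure hospitalizations. The rules under the table count as censored "patients who are lost to follow-up as well as patients who die due to non-cardiovascular causes". SAP 8.2 then builds each pair score "by following the hierarchy of scoring provided in table 1", so the table, not the endpoint list, determines the test statistic.

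SAP 10 states: "The only difference between this SAP 3.0 and protocol rev E is that updated definition of enrolled population for roll-in patients". It mentions no change to the death event.

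**The concern.** Two places in the SAP (Table 1 and the censoring rule) apply the same cardiovascular-only rule, so this is a complete alternative scoring scheme and not a slip in one cell. Followed as written, it tests a composite headed by cardiovascular death while the trial would report one headed by all-cause death.

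Take a Device patient who dies of a non-cardiovascular cause on day 100 and a Control patient alive at one year. Under the declared endpoint, Control wins. Under Table 1 the death decides nothing, and the pair is compared on heart failure hospitalizations up to day 100. If these are equal, the walk test and KCCQ are missing for the dead patient and the pair is a tie. If the survivor had more hospitalizations by day 100, the dead patient wins.

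Non-cardiovascular deaths would then enter a formal comparison only in the all-cause mortality test. That is the last of eight key secondary tests (SAP 8.4), reached only if every earlier test succeeds. The interim conditional-power calculation (SAP 8.10) uses the same test and inherits the ambiguity.

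**Working it through.** **Inputs (SAP 8.11).** One-year mortality in both arms: 20% all-cause, 15% cardiovascular, hence 20% − 15% = 5% non-cardiovascular. Heart failure hospitalizations 0/1/2/3/4/5+: Control 60/10/10/10/5/5%, Device 70/10/5/5/5/5%. Walk-test and KCCQ response: 10% Control, 50% Device. Two-sided alpha 0.05, allocation 2:1, 375 × 0.80 = 300 evaluable, so 200 Device and 100 Control.

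**Assumptions not in the plan.** Death and hospitalization times are uniform over the year. Death, hospitalization and response are independent of each other. There is no dropout beyond death. Walk-test and KCCQ response are taken as independent or as fully dependent, to bracket the unstated correlation.

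**The plan's own power figure.** SAP 8.11 gives 87%. I simulated the SAP 8.2 statistic over all pairs, with 3,000 trials per scenario (Monte Carlo standard error at most √(0.25/3000) = 0.9 points). Power with all-cause scoring was 74.0% (dependent) to 93.4% (independent). With Table 1 scoring it was 80.1% to 96.1%. The 87% lies inside both ranges. It is therefore neither confirmed nor refuted, and it does not reveal which death event was simulated.

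**Deaths affected.** 0.05 × 300 = 15 of 0.20 × 300 = 60 expected deaths, one in four.

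**Cross-arm pairs decided at Step 1.**
- All-cause: 1 − 0.80² = 0.360.
- Table 1: 0.15² (both cardiovascular) + 2(0.15)(0.80) (one cardiovascular death, one survivor) + 2(0.15)(0.05)(0.5) (cardiovascular death precedes the other death) = 0.0225 + 0.240 + 0.0075 = 0.270.
- Simulated: 0.361 and 0.271.

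**A dead patient ranked above a survivor.** Pairs of one non-cardiovascular death and one survivor: 2(0.05)(0.80) = 0.080. The dead patient won in a simulated 0.0157 of all cross-arm pairs, about 310 of 200 × 100 = 20,000. That is 0.0157/0.080 = about 20% of pairs of this kind. With all-cause scoring the share is zero.

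**Test behaviour on the plan's rates.**

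| | All-cause | Table 1 |
|---|---|---|
| Final ties, responses independent | 7.1% | 12.7% |
| Final ties, responses dependent | 14.2% | 19.7% |
| Type I error (Control hospitalization and response rates in both arms, equal mortality) | 4.6% | 4.7% |
| Power, independent | 93.4% | 96.1% |
| Power, dependent | 74.0% | 80.1% |

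**Illustrative imbalances.** These mortality differences are assumed and are not in the plan. Entries are the chance of a significant Device win, independent / dependent responses.

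| Mortality, Device vs Control | All-cause | Table 1 |
|---|---|---|
| Non-CV 7.5% vs 5% | 84.2% / 58.3% | 94.8% / 79.6% |
| Non-CV 10% vs 5% | 69.5% / 39.2% | 94.1% / 76.5% |
| Non-CV 5% vs 10% | 98.2% / 90.4% | 96.0% / 81.0% |
| CV 20% vs 15%, non-CV equal | 68.3% / 39.0% | 75.8% / 45.0% |

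Table 1 scoring barely responds to excess non-cardiovascular death on Device, and it gives little credit for a reduction. When the excess is cardiovascular, the two rules differ much less.

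**The case against.** The strongest reply is that the SAP is contradictory, not settled on cardiovascular death: the all-cause list stands just above Table 1, and an incompletely updated table is a plausible explanation. That is fair as to intent. It does not remove the problem, because the score is defined by reference to Table 1.

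Second, SAP 10 compares the SAP with Protocol revision E, and the revision of the supplied Protocol is not visible. This limits what can be said about a departure from the Protocol. It does not touch the conflict between SAP 3.3 and the SAP 8.2 list on one side and Table 1 and its censoring rule on the other.

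Third, on the plan's rates the numerical effect is small, and the large gaps need mortality imbalances that nothing in the plan suggests. This stands. Those scenarios show what the test would miss; they do not forecast it.

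Fourth, a mortality imbalance would still be seen: SAP 9.1 tabulates all-cause death, with Kaplan-Meier estimates if the data suffice, and the patient-success endpoint requires survival. This also stands, but both are descriptive and neither affects whether co-primary II is met.

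**Conclusion.** The concern holds and must be fixed. The SAP defines level 1 of co-primary II as all-cause death and scores it as cardiovascular death, with no declared change. The textual contradiction needs no calculation.

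On the plan's equal mortality rates the consequences are a quarter of deaths not counted as deaths, 9 percentage points of cross-arm pairs leaving Step 1, and more ties. The power shift is about 2 to 6 points and favours the disputed rule. Type I error is intact in the equal-mortality null that was simulated. The power and tie figures depend on the uniform-timing and independence assumptions and on the walk-test/KCCQ correlation, which the plan does not give. The Step 1 shares follow from the plan's rates, apart from the half-weight given to which of two deaths comes first.

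The main harm is to what the test measures: a difference in non-cardiovascular mortality, including possible device harm, does not count at the level where the trial says it does.

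**What to change.** Make these changes before the interim re-estimation or the final test is run.

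1. In SAP 8.2, Table 1, Step 1, replace cardiovascular cause with any cause in all five lines.
2. Remove deaths from the SAP 8.2 censoring rule. Do the same in Protocol 13.4.2, whose corresponding rule lists dying patients as censored although its own Step 1 scores death as the event. Suggested sense: *Follow-up that ends within the first year for any reason other than death is censored at that time. Death from any cause is the level-1 event and is never a reason for censoring.* The existing shorter-follow-up rule can continue to govern pairs that Step 1 leaves open. Until the Protocol is amended, list this clarification in SAP 10.
3. In SAP 8.10, replace the pointer to section 3.2.2, which does not exist, with the corrected Table 1.
4. In SAP 8.11 and Protocol 13.5, state which mortality rate and what walk-test/KCCQ correlation the 87% power simulation used. Rerun it on all-cause death if cardiovascular death was used. Reconcile the result with the power above 90% given in the Protocol synopsis.
5. As a separate wording correction, the SAP 8.2 sentence limiting comparisons to Device-versus-Control pairs should cover all pairs, as the formula in that section already does.

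If cardiovascular death was in fact intended, the endpoint itself must be amended in Protocol 5.1 and 13.4.2 and in SAP 3.3 and 8.2, and the change declared in SAP 10.

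The cost is SAP wording, one Protocol rule with matching power text, and possibly one simulation rerun. The final test and the conditional-power program must follow the corrected table. No new data are needed.
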